**3.0 Study Endpoints/Events/Outcomes****3.1 Primary Endpoint/Event/Outcome:**

We will obtain a psychophysical (behavioral) measurement of the impact of acute psilocybin intoxication on visual surround suppression in healthy human volunteers. Baseline data will be collected as participants complete the perceptual tasks pre-drug administration. Participants will repeat the tasks again 2 hours after an oral dose of psilocybin, and at 2 week followup.

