## **15.0 Statistical Considerations**

*15.1 Data Analysis Plan:*

For this pilot study, EEG and fMRI data will be analyzed using standard software and toolboxes. EEG data will be processed to eliminate artifacts (e.g., eye movements). EEG signal amplitudes will be analyzed statistically to compare across subject groups and experimental conditions, as with the behavioral data. fMRI data will be analyzed using standard software (e.g. FMRIB Software Library, others) according to standard protocols used previously in psychedelic neuroimaging research (Atasoy et al., 2017; Carhart-Harris et al., 2017b; Deco et al., 2018; Roseman et al., 2018) and human connectome project pipelines used at CMRR. Data will either be analyzed on CMRR secure servers, or on the Minnesota Supercomputing Institute (MSI) servers. Other measures of RMEQ-30, WASI-II, 5D-ASC, EDI, EBI, PANAS, NEO-FFI, HVLT-R, BVMT-R, CSSRS, cytokines, vital signs and diagnostic tests will be analyzed in statistical software programs (e.g. R, SPSS, etc) for significant differences between groups, and assessed for statistically significant relationships with EEG, fMRI and the psychophysics tasks. The team investigators and coordinator will be blinded to condition, however an independent study statistician that will not have any interaction with study participants will perform all blinded data analysis, with unblinded secondary analyses performed by [name], [name] and the study coordinator.

*15.2 Power Analysis:*

Previous work with surround suppression tasks by Co-Investigator (Schallmo et al., 2019) determined the appropriate number of participants with the smallest effect sizes and corresponding standard deviations found that 16 subjects would provide an a priori power of 92% for detecting a significant difference in surround suppression between experimental conditions. Assuming that some drop out may occur, we decided to have 20 participants per drug group (age, sex and baseline clinical variables balanced).

*15.3 Statistical Analysis:*

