We will test hypotheses about differences between baseline EEG signal and psychophysics tasks performed under both psilocybin and the active placebo control during the surround suppression task. We will test changes in primary and secondary endpoints between baseline and each of the drug conditions using univariate repeated measures ANOVA, as well as a mixed-effects regression model (random intercept by participant) controlling for additional co-variates such as treatment order, age, sex, and other relevant predictors at baseline that are significantly different between groups. If diagnostic tests reveal poor adherence to model assumptions, equivalent non-parametric tests will be used instead. We will also test changes in resting state fMRI networks from baseline, and 1-day, 3-days and 7-days after exposure to the experimental compound and placebo control. Will use independent component analysis (ICA) to identify functionally meaningful resting state networks using the FMRIB Software Library (FSL). Significance will be tested at  $p < .05$ .

*15.4 Data Integrity:*

Data collection is the responsibility of the clinical trial staff under the supervision of the site PI. The investigator is responsible for ensuring the accuracy, completeness, legibility, and timeliness of the data reported. All information and data collected from and about participants during the research study will be de-identified and kept in the participants folder in a locked cabinet in a locked room accessible only by research staff. Identifiable forms such as screening forms containing DOB and consent forms will be kept separate from participant data. All research staff and volunteers are required to complete data safety and security and HIPAA training according to University of Minnesota policy. All data electronically stored and transferred will be de-identified and any identifiable pieces of information stored electronically will be kept secure accessible by only research staff and will be encrypted if transferred or using secure portal such as Box.

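### If baseline, psilocybin and niacin share one model, the planned random-intercept and ANOVA analyses pool one error variance, making psilocybin–niacin modestly liberal and niacin–baseline conservative when psilocybin response varies more between people

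*Combined protocol and SAP*

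**What the plan says.** Section 15.3 (Statistical Analysis) describes the comparisons thus: "We will test changes in primary and secondary endpoints between baseline and each of the drug conditions". The methods are a "univariate repeated measures ANOVA, as well as a mixed-effects regression model (random intercept by participant"), the latter adjusted for treatment order, age, sex and baseline imbalances. No sphericity correction, random slope, condition-specific variance or contrast-specific error term is named.

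The one safeguard is conditional: "If diagnostic tests reveal poor adherence to model assumptions, equivalent non-parametric tests will be used instead". The plan names neither the diagnostics nor the replacement tests. The threshold is p < .05, with sidedness not stated.

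Section 3.1 gives the measurement times of the primary endpoint: "Participants will repeat the tasks again 2 hours after an oral dose of psilocybin, and at 2 week followup", in addition to a pre-drug baseline. Section 15.3 does not say whether all conditions enter one model, whether the 2-week follow-up is a level of it, or whether the rows are one summary per person per condition or single task trials.

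**The concern.** With one value per person per condition, a participant random intercept alone imposes equal variances and equal correlations across conditions. A univariate repeated-measures ANOVA whose contrasts use the common mean square makes the same assumption. If some people's perception changes much more under psilocybin than others', that variation enters the psilocybin condition and not the baseline. The pooled error averages it over all conditions: too small for contrasts that carry the extra variance, too large for those that do not.

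The documents give reason to expect such variation. Section 2.2 cites correlations between EEG changes and the intensity of subjective effects. Section 5.2 notes that people higher in neuroticism may be more prone to difficult experiences. Section 15.1 plans to relate the experience scales to the psychophysics and EEG results.

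At stake are the true error rate of psilocybin versus niacin, which is the comparison in the stated purpose (Section 1.0), and the power to see whether the active placebo itself shifts the task. An over-wide niacin–baseline interval could make the control look inert.

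**Working it through.** **The plan's own figure.** Section 15.2 says "16 subjects would provide an a priori power of 92" per cent, based on the "smallest effect sizes and corresponding standard deviations" from earlier work. Neither effect size nor SD is given, so the figure cannot be reproduced, only solved backwards. With a paired two-sided t test at 0.05 (noncentral t, noncentrality dz × √n), n=16 and 92% power imply dz ≈ 0.90. At n=40 that effect has power above 99%. This shows what a moderate change in error rate could do to the main psilocybin result, but it says nothing about variance by condition.

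**Inputs.** N=40, 20 per sequence (Sections 5.1 and 5.3). Two-sided alpha 0.05 (sidedness assumed). k=3 conditions in one model (assumed). Residual variance s² in each condition, set to 1. Extra between-person variance t² under psilocybin. No ratio is available, because Section 2.1 reports no preliminary data, so two are assumed:

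- psilocybin SD ratio 1.5: t² = 1.5² − 1 = 1.25
- psilocybin SD ratio 2: t² = 2² − 1 = 3

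**Formulas.** The true variance of a within-person difference is 2s² + t² for psilocybin versus baseline or niacin, and 2s² for niacin versus baseline. The pooled model uses 2s² + (2/k)t² for all three. In large samples the actual type I error is 2 × [1 − Φ(1.96 × √(pooled/true))].

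**Only psilocybin adds variance, k=3.**

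| SD ratio | Pooled variance | Psilocybin contrasts: pooled/true | Type I error | Niacin–baseline: pooled/true | Type I error |
|---|---|---|---|---|---|
| 1.5 | 2 + 0.833 = 2.833 | 2.833/3.25 = 0.872 | 6.7% | 2.833/2 = 1.417 | 2.0% |
| 2 | 2 + 2 = 4 | 4/5 = 0.800 | 8.0% | 4/2 = 2.000 | 0.6% |

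Simulation of the pooled-error contrasts at N=40 agrees with this formula. Contrasts that use their own error stay at 5%.

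**Niacin response also varies, with extra variance t²/2.** Pooled variance is 2 + (2/3)(1.5t²) = 2 + t², which equals the true psilocybin–baseline variance, so that contrast returns to 5%. Psilocybin–niacin has true variance 2 + 1.5t²:

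- SD ratio 1.5: 3.25/3.875 = 0.839, type I error 7.3%
- SD ratio 2: 5/6.5 = 0.769, type I error 8.6%

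Niacin–baseline, with true variance 2 + t²/2, stays conservative: 3.25/2.625 = 1.238 gives 2.9%, and 5/3.5 = 1.429 gives 1.9%.

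**Power for niacin–baseline.** If only psilocybin adds variance, a niacin effect with 80% power under its own error has about 73%, 63% and 45% power under the pooled error at t²/s² = 1, 2 and 4.

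**Greenhouse-Geisser.** At N=40, k=3 and t²/s² = 4, the uncorrected omnibus test has error 6.3% and the corrected one 4.9%. Contrasts that use the pooled mean square are unchanged by the correction.

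**Cost if variances are equal.** The critical t is 2.023 on 39 df (own error) against 1.991 on 78 df (pooled). 2.023/1.991 = 1.016, so intervals are about 1.6% wider.

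**The case against.** The strongest reply is that Section 15.3 speaks of changes between baseline and each drug condition, which can be read as two separate two-level comparisons. With two levels and complete data, both planned methods reduce to the paired t test and nothing is pooled. This stands, and it is why the point is conditional. A joint model is at least as natural a reading, because the same section describes one regression adjusted for treatment order. Separate baseline comparisons would also leave psilocybin versus niacin untested.

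Second, the plan has a diagnostics clause and does not exclude a sphericity correction. Both are true. A paired rank test would avoid the pooled error, but the clause names no check, threshold or test, so it cannot be relied on to resolve this.

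Third, the variance ratios are assumed and the effect is moderate. At t² = s² the psilocybin error is about 6.4%, and 1,000 fitted random-intercept models there gave 5.1% and 4.9%, within about two Monte Carlo standard errors of both 5% and 6.4%. If the true effect is near dz 0.90, the main psilocybin conclusion would rarely turn on this. That also stands. The exposure is to smaller effects, the secondary EEG endpoint, interval width and the niacin comparison.

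Three stronger readings go beyond the documents:

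- A reader might infer that every psilocybin contrast is liberal. That requires psilocybin alone to add response variance. With niacin at half the extra variance, psilocybin–baseline is at 5%.
- Adding the 2-week follow-up as a fourth level raises psilocybin error to 7.4–11.1% for t²/s² from 1 to 4. Section 3.1 lists that time point, but nothing in Section 15.3 puts it in this model.
- If single trials were the rows, the error could be far higher: about 29% with an assumed 100 trials per condition and person-by-drug variance at 5% of trial variance. The plan does not say that trials are the rows. This is a reason to ask for the unit, not a finding.

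**Conclusion.** The point holds as a conditional and moderate one. It needs baseline, psilocybin and niacin in one model, one value per person per condition, and greater between-person variation in response to psilocybin than to niacin. Under the assumed SD ratios of 1.5 and 2 at N=40, with only psilocybin adding variance, type I error is about 6.7% and 8% for psilocybin contrasts, and about 2% and 0.6% for niacin versus baseline. Psilocybin versus niacin stays liberal even when niacin response varies half as much; psilocybin versus baseline does not. It would be wrong to conclude that the stated 5% level fails whatever the data look like, or that the primary result is unsafe: with equal variances or separate two-level models the level is correct. The case for changing the plan is that the alternative is valid whether or not the variances differ, and costs very little.

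**What to change.** In Section 15.3:

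1. State the analysis unit (one suppression index per person per condition) and which conditions enter the model, including whether the 2-week follow-up does.
2. Replace the random-intercept structure with an unstructured covariance across conditions, so that each condition has its own variance, with Kenward-Roger degrees of freedom. Alternatively, test each contrast on within-person differences adjusted for period. The two are not identical: the difference analysis uses only participants with both sessions, whereas the mixed model keeps those with one.
3. If the ANOVA is kept, apply Greenhouse-Geisser to the omnibus test only, and test each contrast with its own error term. The correction alone would leave the contrasts as they are.

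The cost is a few lines of text and a changed model statement. With three conditions the unstructured matrix has six parameters against two, so four more to estimate. If variances are in fact equal, intervals widen by about 1.6%.

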4.3 Biosafety: N/A

4.4 Stem Cells: N/A

4.5 Fetal Tissue: N/A

## 5.0 Procedures Involved

### 5.1 Study Design:

The study involves a randomized, double blind, placebo controlled, crossover design with two different groups pairing the psychoactive drug psilocybin, or the active placebo Niacin, with a combination of perceptual tasks.

Randomization and Double-Blind: Participants who meet criteria for entry into the study (based on the telephone screen and the clinical interview) and consent to participate will be randomized to *psilocybin first (group A) or niacin first (group B)*, using an adaptive minimization randomization method. The purpose of the procedure is to ensure that the 2 groups are similar with respect to *age and gender*. Specifically, the minimization procedure will balance age groups (45 years or below/above 45 years) and gender. Following the evaluation, the study coordinator will share numerical values for these variables along with the subject ID number through a secure system (Box Secure Storage) with the study statistician who will use participant information to assign a blinded randomization group (A or B) using the minimization procedure.

The study statistician will then pass the blinded group assignment to IDS. Before the first participant is randomized, IDS will randomly assign “psilocybin first” “niacin first” to the letters A, and B; this assignment (of group to treatment letter) will not be communicated to anyone outside of IDS until the study is complete and the study team is ready to break the blind. Randomization will occur after Visit 1 (Day 0), when it is confirmed all eligibility criteria are met and before Visit 2, with a maximum 30-day window between them.

Participants will have one training/baseline session, followed by 2 experimental sessions in randomized order for each of the drug conditions (psilocybin or niacin placebo). We will test subjects under the influence of 25mg of psilocybin (**condition 1**) or 100mg of active placebo control (niacin or, **condition 2**).

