We will test two groups for each of these conditions. Group A will be given psilocybin first, and active placebo Niacin second (N=20) and tested on surround suppression and EEG recording starting at 2 hours after ingestion of the experimental compound. Group B will be given niacin on their first dosing day and psilocybin on their second dosing day (N=20) and tested on surround suppression and EEG recording starting at 2 hours after ingestion of the experimental compound.

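### Section 15.3 names no period (first versus second dosing visit) effect in the crossover model; the covariates it does name are constant within a participant and leave the psilocybin-niacin contrast essentially unchanged

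*Combined protocol and SAP*

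**What the plan says.** Section 5.1 of the combined protocol and SAP sets out the design: "The study involves a randomized, double blind, placebo controlled, crossover design with two different groups". The groups are the two sequences: "Group A will be given psilocybin first, and active placebo Niacin second (N=20"), and "Group B will be given niacin on their first dosing day and psilocybin on their second dosing day (N=20"). One training/baseline session precedes both dosing visits. Allocation is by minimisation, in which "the minimization procedure will balance age groups (45 years or below/above 45 years) and gender".

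Section 15.3 gives the analysis: "We will test changes in primary and secondary endpoints between baseline and each of the drug conditions using univariate repeated measures ANOVA", together with a "mixed-effects regression model (random intercept by participant"). The adjustment planned for that second model is worded as "controlling for additional co-variates such as treatment order, age, sex, and other relevant predictors at baseline that are significantly different between groups". On the error rate it says "Significance will be tested at" the 0.05 level, without stating sidedness. No period, visit or session term is named there or elsewhere, nor is a treatment-by-order interaction, which would be equivalent to one.

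Section 15.2 expects some dropout but gives no rate. It states 92% power with 16 subjects and gives neither the effect size nor the SD.

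**The concern.** The drug effect in this trial is a within-participant comparison, so the adjustments that matter are those that differ between a participant's two dosing visits. Age, sex, a single pre-dosing baseline value and sequence do not differ between them. The visit's place in the series does.

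The documents give reasons to expect a difference between the two visits. The task is repeated, section 5.2 describes it as assessing learning as well as perception, and preparation is 8 hours before the first dosing but 1 hour before the second. If such a shift exists and is not modelled, it goes into the residual variance and costs precision. If the sequences end up unequal, part of it leaks into the drug contrast.

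Choosing further covariates because they differ significantly between randomised groups leaves the final model open until data are seen and gives the contrast nothing in return.

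**Working it through.** **Inputs.** From the documents: two sequences of 20, a random participant intercept, the listed covariates, alpha 0.05 (two-sided assumed), and 92% power with 16 subjects. Assumed, because the documents give none: the period effect, the drug effect, the SDs and the dropout counts.

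**The plan's own figure.** The 92% cannot be reproduced without an effect size and SD. Solving backwards for a paired two-sided t-test with n=16 gives a standardised paired effect d_z = 0.90.

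**Why the listed terms drop out.** Let δ be the psilocybin-minus-niacin effect, π the shift from first to second dosing visit, and γz a participant-level term. The paired difference (psilocybin minus niacin) has mean:

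- Group A, psilocybin first: (δ + γz) − (π + γz) = δ − π
- Group B, niacin first: (δ + π + γz) − γz = δ + π

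The term γz cancels and π does not. A sequence main effect is one of the γz terms, so it does not remove π.

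**Check by fitting.** I fitted REML random-intercept models to simulated trials (60 per scenario, π = 0.5, within-visit SD 0.7). The SE columns give the mean standard error of the drug contrast.

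| Scenario | Largest shift in estimate from adding order, age, sex, baseline | SE, drug only | SE, plus covariates | SE, plus period |
|---|---|---|---|---|
| 20/20 complete | below 10⁻¹⁴ | 0.1742 | 0.1742 | 0.1536 |
| 20/20, baseline rows kept | below 10⁻¹⁴ | 0.1662 | 0.1662 | 0.1558 |
| 22/18 complete | below 10⁻¹⁴ | 0.1743 | 0.1743 | 0.1544 |
| 20/16 complete | below 10⁻¹⁴ | 0.1833 | 0.1833 | 0.1625 |
| 4 of 40 lose second visit | 0.08 (mean 0.017) | 0.1822 | 0.1817 | 0.1608 |
| 8 of 40 lose second visit | 0.12 (mean 0.023) | 0.1907 | 0.1897 | 0.1689 |

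**Loss of precision at 20/20.** Let q = π / SD of the paired difference. Without a period term, the variance of the pooled differences is about SD²(1 + q²), so the standard error is inflated by √(1 + q²). At q = 0.5 this is √1.25 = 1.118, equivalent to 40/1.25 = 32 participants. With baseline rows in the model the inflation is smaller: 0.1662/0.1558 = 1.067 in the table.

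Power and type I error by Monte Carlo (N=40, 20/20, paired analysis, 40,000 runs):

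| q | Power without period, d = 0.5 | Power with period | Type I error without period |
|---|---|---|---|
| 0 | 87% | 87% | 5.1% |
| 0.25 | 85% | 87% | 4.3% |
| 0.5 | 81% | 87% | 2.9% |
| 0.75 | 73% | 87% | 1.4% |

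At d_z = 0.90 and N=40, power without period is 99.9% at both q = 0.5 and q = 0.75, against 99.98% with it.

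**Bias with unequal sequences.** With complete pairs, bias = π(nB − nA)/(nA + nB).

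- 20/20: 0
- 22/18: −4/40 = −0.10π
- 20/16: −4/36 = −0.11π

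If four Group B participants lose only their second visit and their earlier data are kept, generalised least squares gives a bias of 7.2% to 9.4% of π for an intraclass correlation of 0.3 to 0.7, or 6.8% to 7.8% when baseline rows are also in the model.

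**The significance screen.** The chance that at least one of k independent baseline variables differs at 0.05 between randomised groups is 1 − 0.95^k: 23% for k = 5 and 40% for k = 10.

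**The case against.** **The plan does not exclude a period term.** The covariate list is open-ended, and treatment order is never defined. Section 4.2 mentions testing group and order as two separate things. In a data set with one row per session, order coded first/second would be the period term. A reader might infer that the plan leaves period out by decision; the documents do not show that. What stands is that section 5.1 defines the groups by which drug comes first, so order most naturally means sequence, and two analysts could fit different models from the same text.

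**The stakes may be small.** With balanced sequences the omission makes the test conservative, so no false-positive risk is shown. On the effect size implied by the stated power, the loss is under one point. The training session should absorb some early learning. Section 12.2 keeps data collected before withdrawal, which reduces the bias below the complete-pairs figure. All of this stands and limits the size of the point. A reader might infer that the trial is underpowered or its primary contrast seriously biased, and the documents support neither. Even 11% of a 0.5 SD period effect is 0.056 SD, about a third of one standard error.

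**If the covariates do nothing, selecting them does no harm, and the proposed sequence, age-group and gender terms do nothing either.** For the drug contrast with complete pairs this is correct. The objection to the screen is therefore that it leaves the model undetermined without benefit; distortion of the contrast is not shown. Sequence and the minimisation factors belong in the list because they describe the design and can be fixed beforehand. Under dropout they have only the small influence shown in the table.

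**Conclusion.** The point holds as a gap in the specified crossover model. Read in its most natural sense, section 15.3 adjusts for terms that leave the psilocybin-niacin contrast and its standard error unchanged when both visits are observed, and does not name the one nuisance term that would change them. Followed that way, the plan gives an unbiased contrast at 20/20 with a standard error that is too large. With unequal sequences it adds a small bias, at most about 11% of the period effect in the cases examined.

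The practical loss depends on quantities the documents do not give. At N=40 and a 0.5 SD drug effect, it is about 6 power points for a 0.5 SD period effect and about 14 for 0.75 SD. For a drug effect near 0.90 SD it is negligible. The change is worth making because it settles an ambiguity and protects precision at almost no cost. No invalid result is shown to follow from the current text.

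**What to change.** In section 15.3, replace the open covariate list with a fixed model:

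- fixed effects for drug condition, period (first or second dosing visit) and sequence;
- the minimisation factors from section 5.1 (age group split at 45, gender);
- a random participant intercept.

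State that treatment order means sequence. Delete the selection of covariates by baseline significance. Report the psilocybin-niacin contrast from this model.

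The cost is a rewording and one degree of freedom for the period term (39 to 38 in the paired analysis of 40 participants). With no period effect, power is the same to within 0.1 point. Visits, procedures and data collection do not change.
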